13.3 Study Oversight

This protocol will adhere to the policies and requirements listed in [Appendix B](#). The specific responsibilities of the PI, the ION Coordinating Center and NeoImmuneTech and the procedures for auditing are presented in [Appendix B](#).

- The contract research organization (CRO), IQVIA, is responsible for distributing all Investigational New Drug Application (IND) Action Letters or Safety Reports received from

the study sponsor, NeoImmuneTech, to all participating institutions for submission to their individual Institutional Review Boards (IRBs) for action as required.

- Investigational agents may be ordered by a participating site only after approved by the study sponsor, NeoImmuneTech, and officially activated by the ION Coordinating Center.

14. SITE ACTIVATION PROCEDURES

14.1 IRB Approval

Each investigator or group of investigators at a clinical site must obtain IRB approval for this protocol and submit all required regulatory documents (including any protocol-specific documents) to the CRO, IQVIA, before they can be approved to enroll patients. IQVIA uses extensive data to make a determination of whether a site has fulfilled all regulatory criteria including but not limited to:

- An active Federal Wide Assurance (FWA) number
- A complete Delegation of Duties Sheet (which must be maintained and kept current)
- A valid IRB approval
- Compliance with all protocol-specific requirements

In addition, the site-protocol PI must meet the following criteria:

- Complete Form FDA 1572
- Complete Financial Disclosure
- Current Curriculum Vitae
- Valid Medical License

Evidence of the following training must be provided for the site-protocol PI, sub-investigators and all participating clinical site staff, as reported on the Form FDA 1572 and Delegation of Duties Sheet:

- Current GCP Training
- Current Human Subject Protection (HSP) Training
- Evidence of Protocol/Amendments Training

14.1.1 *Submitting Regulatory Documents*

Submit your IRB approval, model Informed Consent Form (ICF), and other protocol-specific regulatory documentation to IQVIA, where they will be filed and tracked.

Regulatory Submission of Essential Documents (pre-site activation) to IQVIA by e-mail to [contact].

14.2 Patient Enrollment

Patient enrollment will be facilitated using the enrollment module in the EDC system. To access the enrollment module, the site user must be assigned the ‘Enroll/Randomize participants’ responsibility on the ION Delegation of Duties Sheet.

Before enrolling a patient in the EDC system, registration staff should verify the following:

- All eligibility criteria have been met within the protocol stated timeframes.
- If applicable, all patients have signed an appropriate consent form and Health Insurance Portability and Accountability Act of 1996 (HIPAA) authorization form (if applicable).

For further instructional information on patient enrollment; please refer to the Study Procedures Manual or contact the ION Coordinating Center at [contact].

14.3 General Guidelines

After enrollment, patients should begin protocol treatment within 3 business days. Issues that would cause treatment delays should be discussed with the PI. If a patient does not receive protocol therapy after enrollment, the patient’s enrollment on the study may be canceled. The Clinical Research Site (CRS) must notify the ION Coordinating Center of cancellations as soon as possible.

15. STATISTICAL CONSIDERATIONS

This section outlines the statistical analysis strategy and methods for the study. If, after the study has begun, but before the conduct of any analysis, changes are made to primary and/or key secondary hypotheses or the statistical methods related to those hypotheses, then the protocol will be amended (consistent with ICH Guideline E-9). Changes to exploratory or other non-confirmatory analyses made after the protocol has been finalized, along with an explanation as to when and why they occurred, will be listed in the Clinical Study Report (CSR) for the study. Post hoc exploratory analyses will be clearly identified in the CSR. No separate Statistical Analysis Plan (SAP) will be issued for this study.

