3. OBJECTIVES AND ENDPOINTS

This study will evaluate the safety and tolerability and assess the antitumor efficacy of NT-I7 in combination with atezolizumab (Phase 1b/2a) in patients with anti-PD-1/PD-L1 naïve or relapsed/refractory high-risk skin cancers (cSCC, MCC, melanoma). Specific objectives and corresponding endpoints for the study are outlined in Table 2.

Table 2 – Study Objectives and Endpoints

Objectives	Corresponding Endpoints
Primary Objective	

To evaluate the safety and tolerability of NT-I7 in combination with atezolizumab (Phase 1b), including estimation of the Maximum Tolerated Dose (MTD) and/or the Recommended Phase 2 Dose (RP2D)
 
Phase 2a: To evaluate the Objective Response Rate (ORR) according to RECIST v1.1 and iRECIST, as determined by the investigator
	
 - Incidence, nature, and severity of adverse events graded according to NCI CTCAE v5.0 - Incidence and nature of DLTs - Potential correlation with PK, pharmacodynamic, safety, and efficacy parameters - Objective Response Rate (ORR), defined as the percentage of patients who have at least one confirmed partial response (PR) or complete response (CR) according to RECIST v1.1 and iRECIST, as determined by the investigator
Secondary Objectives	

To evaluate immunogenicity of NT-I7 in combination with atezolizumab
 
To make a preliminary assessment of the anti-tumor activity of NT-I7 in combination with atezolizumab
	
 - Incidence of anti-drug antibody (ADA) to NT-I7 during the study relative to the prevalence of ADA at baseline - Disease Control Rate (DCR), defined as proportion of patients with a best overall response of CR, PR or stable disease (SD). - Duration of objective response (DOR), defined as the time from the first occurrence of a documented objective response to the time of the first documented disease progression or death from any cause, whichever occurs first, per RECIST v1.1 and iRECIST as determined by the investigator - Progression Free Survival (PFS), defined as the time from the first study treatment (Cycle 1, Day 1) to the first occurrence of progression or death from any cause, whichever occurs first, per RECIST v1.1 and iRECIST as determined by the investigator - Overall survival (OS), defined as the time from first study treatment (Cycle 1, Day 1) to death from any cause
Exploratory Objectives	

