15.4 Stratification Factors: N/A

15.5 Analysis of Secondary Endpoints

15.5.1 Secondary Objectives

Statistical analyses will be conducted for the following secondary objectives:

- The immunogenicity of NT-I7
- A preliminary assessment of the anti-tumor activity of NT-I7 in combination with atezolizumab, including the ORR, as measured by RECIST v1.1 and iRECIST, the DCR, DOR, PFS, and OS.

Descriptive statistics will be provided. Mean, standard deviation, median, minimum and maximum will be displayed for continuous variables, and numbers and percentages will be displayed for counts and binary variables. Kaplan-Meier estimates will be considered for time to event variables (DOR, PFS and OS). The analyses will be performed for each arm in Phase 2a, separately.

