1.2.3. Exploratory Objectives

- To make a preliminary assessment of pharmacokinetic (PK) parameters of NT-17 in combination with atezolizumab
- To make a preliminary assessment of biomarkers that might act as pharmacodynamic indicators of activity of NT-17 in combination with atezolizumab
- To make a preliminary assessment of biomarkers that might act as predictors of anti-tumor activity of NT-17 in combination with atezolizumab

This statistical analysis plan (SAP) describes the populations for analysis, data handling rules including handling of missing data and imputation, statistical methods, and table/listing/figure formats for data presentation ("TLF shells"). The statistical analyses and summary tabulations prepared according to this SAP will provide the basis for the results sections of the CSR for this trial.

This SAP also will outline any differences in the currently planned analyses relative to those planned in the study protocol.

Sponsor:	NeolimmuneTech, Inc.		
Protocol:	NTT-106 (ION-02)		
Document Version No.:	1.0	Document Date:	20Nov2023

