2.5. Efficacy, Pharmacokinetic, and Safety Variables

2.5.1. Efficacy Variables

- Objective Response Rate (ORR) defined as the percentage of patients who have at least one confirmed partial response (PR) or complete response (CR) according to Response Evaluation Criteria in Solid Tumors (RECIST) v.1.1
- Disease Control Rate (DCR) defined as the percentage of patients with a response of CR, PR or stable disease (SD) according to RECIST v.1.1
- Progression Free Survival (PFS) defined as the time from the first study treatment to the first occurrence of progression, as measured by RECIST v.1.1 or death from any cause, whichever occurs first
- Overall survival (OS) defined as the time from first study treatment to death from any cause.
- Duration of stable disease (DOSD) defined as the time from the first occurrence of stable disease or better (PR or CR or SD) to the time of the first documented disease progression or death from any cause, whichever occurs first per RECIST v.1.1

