5. CHANGES TO PLANNED ANALYSES

Due to the premature closure of the study the following changes are made in comparison to the protocol:

- AEs leading to withdrawal and DLTs will not be listed separately.
- Laboratory values will only be listed.
- irRC (iRECIST) will not be summarized.
- Efficacy summaries will be performed on Efficacy Population only.
- All phases will be summarized within the same table.
- Duration of Stable Disease will replace Duration of Response analysis, due to limited patient responses.

Sponsor:	NeolimmuneTech, Inc.		
Protocol:	NIT-106 (ION-02)		
Document Version No.:	1.0	Document Date:	20Nov2023

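### SAP Section 5 replaces the pre-specified secondary endpoint DOR with duration of stable disease because few responses were seen; the swap is declared, but it is undated, not marked post hoc where it is used, and leaves no DOR output

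*Protocol*

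**What the plan says.** Protocol Table 2 lists among the secondary endpoints "Duration of objective response (DOR), defined as the time from the first occurrence of a documented objective response", running to progression or death, under RECIST v1.1 and iRECIST. Section 15.5.1 repeats it within the anti-tumor assessment, "including the ORR, as measured by RECIST v1.1 and iRECIST, the DCR, DOR, PFS, and OS". It then sets out the method, by Phase 2a arm: "Kaplan-Meier estimates will be considered for time to event variables (DOR, PFS and OS". Section 2.1 also counts DOR among the outcomes on which the trial is to show an increase, and SAP Section 1.1 carries that statement over.

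SAP Section 5 opens with "Due to the premature closure of the study the following changes are made in comparison to the protocol". The last of its six items is "Duration of Stable Disease will replace Duration of Response analysis, due to limited patient responses". SAP Section 2.5.1 then lists, beside ORR, DCR, PFS and OS, "Duration of stable disease (DOSD) defined as the time from the first occurrence of stable disease or better (PR or CR or SD". Section 4.8.4 gives DoSD a median, Kaplan-Meier estimates and a plot. Neither section has a DOR variable or output.

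On disclosure, protocol Section 15 asks that changes to non-confirmatory analyses be listed in the clinical study report (CSR) with when and why they occurred. It continues: "Post hoc exploratory analyses will be clearly identified in the CSR. No separate Statistical Analysis Plan (SAP) will be issued for this study". SAP Section 1.2.3 makes the SAP outputs the basis of the CSR results and adds: "This SAP also will outline any differences in the currently planned analyses relative to those planned in the study protocol".

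**The concern.** A duration endpoint has been exchanged after response data were known, and the number of responses is the stated reason. The list as a whole is attributed to early closure, but this is the only item with a reason of its own, and that reason is efficacy data from an open-label, investigator-assessed trial.

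Two things are at stake. First, the protocol undertook to report how long responses last, and the SAP plans no summary or derived listing that does so. Second, DoSD will have patients in it when DOR is nearly empty. Placed among the ordinary efficacy variables without a post hoc label, it could be read as the planned durability result.

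**Working it through.** **1. The plan's own figures.** The documents attach no number to DOR or DoSD. The only sample-size figures are the ORR thresholds in Protocol 15.3 and SAP 4.1, and both reproduce with exact (Clopper-Pearson) 95% intervals.
- 17/24 gives 48.9% to 87.4%, which excludes 45.25%. 16/24 has a lower limit of 44.7%, which does not.
- 6/36 gives 6.4% to 32.8%, which excludes 5%. 5/36 has a lower limit of 4.7%, which does not.

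The point does not depend on these thresholds, but the reference rates give a sense of scale. At full enrolment, expected responders at those rates are 24 x 0.4525 = 10.9 in Arm I and 36 x 0.05 = 1.8 in Arm II. The design therefore already allowed for very few responders in Arm II if the combination added nothing, and DOR was still specified by arm.

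**2. The definitions side by side.**

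| | DOR (Protocol Table 2) | Duration of SD (Protocol 11.1.6) | DoSD (SAP 2.5.1, 4.8.4) |
|---|---|---|---|
| Who | Responders | Patients with SD | Patients with CR, PR or SD |
| Start | First documented response | Start of treatment | First recorded CR, PR or SD |
| End | Progression or death | Progression | Progression or death |
| Status | Secondary endpoint | Defined, not a Table 2 endpoint | Efficacy variable, no post hoc label |

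DoSD matches neither protocol definition.

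**3. Effect on a responder's clock.** Under Protocol 6.7 the first two scans are 9 ± 1 weeks apart. Take a patient with SD at the first scan and PR at the second. DoSD starts one interval before DOR, which adds 9 x 7 / 30.4375 = 2.1 months (8 weeks: 1.8; 10 weeks: 2.3). A patient whose first assessment is already a response gains nothing. DoSD therefore cannot be converted back to DOR without patient-level response dates.

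**4. Effect of the mixture.** The share of DoSD patients who never responded is (DCR - ORR) / DCR. The observed rates are not in the documents, so the inputs are assumptions.
- ORR 20%, DCR 40%: 20/40 = 50%.
- ORR 20%, DCR 50%: 30/50 = 60%.
- ORR 5%, DCR 40%: 35/40 = 87.5%.
- ORR 5%, DCR 50%: 45/50 = 90%.

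**5. What is left on responders.** SAP 4.8.1 keeps listings of tumor and response assessments, and SAP 4.2.8 puts all CRF data into listings. No listing carries a derived response start, end date or event/censor flag, and no DOR summary is specified.

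**6. What is disclosed.** SAP 5 gives the change and the reason. It does not say when the decision was made or what response data had been reviewed by then.

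**The case against.** The strongest defence is that nothing is hidden. The exchange sits under a heading for changes to planned analyses, with its reason, in a study that closed early, where trimming descriptive output is natural. ORR and every best-response category are still tabulated (SAP 4.8.1), and PFS and OS keep their curves. No p-values are reported (SAP 4.2.5). The protocol said only that Kaplan-Meier estimates would be considered. With a handful of responders a median may not be estimable. Protocol 11.1.6 already has a duration of stable disease. All of this stands, and it limits the point.

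It also rules out several stronger readings that a reader might infer:
- **That the swap enters the CSR unlabelled.** SAP 5 declares it, protocol Section 15 requires it to be explained in the CSR, and the CSR is not among the documents.
- **That an unfavourable result is being suppressed.** The response rate itself is still reported in full.
- **That response durability goes wholly unreported.** Assessments are listed by patient, and responders are counted within DoSD, mixed with SD patients.
- **That the protocol's amendment duty was breached.** That duty concerns primary and key secondary hypotheses. DOR has no hypothesis and is not called key secondary.

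The defence does not answer the core of the point. Declaring a substitution does not restore the endpoint, early closure is not the reason given for this item, and small numbers do not prevent a listing.

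**Conclusion.** The point holds as a gap in output and labelling. A pre-specified secondary endpoint is dropped for a reason drawn from observed responses. Its replacement measures something else and is not marked post hoc where it is defined and analysed. The timing of the decision relative to data review is not given.

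Planned DOR summaries and derived listings fall to zero. For a patient who is stable at the first scan and responds at the second, DoSD exceeds DOR by about 2.1 months (1.8 to 2.3). The 50-90% non-responder share rests wholly on the assumed ORR of 5-20% and DCR of 40-50%. It shows how far the mixture could go and says nothing about what this trial observed. No error rate is affected, because the analyses are descriptive.

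**What to change.** - **SAP 5:** reword the last item so that DoSD is added and DOR is kept. State when the change was decided and that response data were known.
- **SAP 4.8:** keep DOR as defined in Table 2, under RECIST v1.1 only, since SAP 5 already drops iRECIST summaries. Give a listing of every confirmed responder with response date, end date and event/censor flag. Add a Kaplan-Meier median with 95% CI, or an entry that it is not estimable.
- **SAP 2.5.1 and 4.8.4, the tables, listings and figures, and the CSR:** label DoSD post hoc, and note that its start differs from protocol 11.1.6.
- **Protocol Section 15 (minor and separate):** reconcile the statement that no SAP will be issued with the SAP that exists.

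The cost is one short listing and some wording. The data are already collected. The only downside is a median that may turn out not to be estimable.

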15.1 Responsibility for Analyses

The statistical analysis of the data obtained from this study will be the responsibility of Fred Hutch as part of the ION.

15.2 Study Design/Objectives

The proposed clinical trial is a phase 1b/2a, open-label, multicenter study of the administration of atezolizumab (MPDL3280A) in combination with NT-I7 in patients with anti-PD-1/PD-L1 naïve or relapsed/refractory high-risk skin cancers: cSCC, MCC and melanoma.

This study will evaluate the safety and anti-tumor activity of NT-I7 in combination with atezolizumab, including estimation of the MTD and/or the RP2D. The trial is designed to

determine whether NT-I7, at doses known to increase the peripheral blood T-cell level, will also increase the level of tumor infiltrating T-cells and thereby increases the efficacy of atezolizumab.

15.2.1 *Dose Escalation Phase*

A 3+3 dose escalation design will be utilized. Four pre-specified doses of NT-I7 (120, 360, 840, and 1200 µg/kg) will be tested (refer to Section 5). The initial dose level will start at 120 µg/kg. NT-I7 doses will be escalated according to the dose escalation scheme in Section 5.2.2, 1200 µg/kg as the MAD. Enrollment will continue until the MTD or RP2D is identified, or up to the MAD.

The RP2D will be selected according to the following logic, taking into account the MTD determination from the Dose Escalation Phase (Phase 1b) and the MED level which is defined as the dose level at which maximum effects on peripheral blood T-cell levels and intratumor T-cell levels are observed. The intratumor T-cell levels will dominate if the peripheral blood and intratumor T-cell levels differ. The available data will be assessed by the Data and Safety Monitoring Committee, which includes the ION Coordinating Center, the Protocol PI, clinical sites PIs and NeoImmuneTech's Chief Medical Officer or designee to select the RP2D.

- If the MTD is determined AND
 - MTD = MED, then the RP2D = MTD = MED
 - MTD > MED, then the RP2D = MED
- If the MTD is not reached, then the RP2D = MED
- Once the RP2D has been selected, the trial will proceed to the Dose Expansion Phase (Phase 2a) to further evaluate RP2D in a larger number of patients.

15.2.2 *Expansion Phase*

The selected RP2D will be further evaluated in the Phase 2a.

The Phase 2a is designed to evaluate the anti-tumor effects of NT-I7 in combination with atezolizumab in a total of 60 patients. Twenty-four patients in Arm I, i.e., 12 patients for each indication (cSCC and MCC), and 36 patients in Arm II, i.e., 12 patients for each indication (MCC, cSCC and melanoma), will be enrolled. Enrolled patients will be separated into 2 arms depending on previous use of anti-PD-1/PDL-1 therapy and cancer type (see Section 5).

15.3 **Sample Size/Accrual Rate**

During the dose escalation phase (Phase 1b), a 3+3 design will be used for identifying the MTD and/or the RP2D. The following design will be used:

Number of Patients with DLT at a Given Dose Level	Escalation Decision Rule
0 out of 3	Enroll 3 patients at the next dose level.
1 out of 3	Enroll at least 3 more patients at this dose level. 
 • If 0 of these 3 additional patients experience a DLT (totaling 1/6), escalate to the next dose level. • If ≥ 1 of these 3 additional patients experiences DLT (totaling $\geq 2/6$ at the dose level), the dose escalation is stopped, and the next lower dose level will be declared the MTD. In the case this happens at the 120 $\mu\text{g}/\text{kg}$ dose level, a lower dose of 60 $\mu\text{g}/\text{kg}$ will be tested, and the same 3+3 design followed.
≥ 2 out of 3	Dose escalation will be stopped. The next lower dose level will be declared the MTD. Three (3) additional patients will be entered at the next lower dose level if only 3 patients were treated previously at that dose. In the case this happens at the 120 $\mu\text{g}/\text{kg}$ dose level, a lower dose of 60 $\mu\text{g}/\text{kg}$ will be tested, and the same 3+3 design followed.

Abbreviations: DLT=dose-limiting toxicity; MTD=maximum tolerated dose.

Once all patients in a cohort have completed the 3-week DLT window, all AEs will be assessed by the Data and Safety Monitoring Committee.

In the dose expansion phase (Phase 2a), a total of 60 patients will be treated at the RP2D as defined above.

Based on the available data provided in Section 2.2, the average historical ORR for the patients in this study would be 45.25% in Arm I and less than 5% in Arm II. With a total of 24 patients treated at the RP2D in Phase 2a of the study in Arm I, the 95% confidence interval for an observed ORR of 17/24 or higher would exclude 45.25%. With a total of 36 patients treated at the RP2D in Phase 2a of the study in Arm II, the 95% confidence interval for an observed ORR of 6/36 or higher would exclude 5%.

Approximately 84 patients will be enrolled in this study; up to approximately 24 patients in the Phase 1b and approximately 60 evaluable patients in the Phase 2a of the study. The expected accrual is 4 patients per month total at approximately 8 ION sites.

Safety Population: All patients who receive at least 1 dose of the investigational regimen will be considered evaluable for safety and included in the overall safety analysis. For the Phase 1b, in the absence of a DLT, patients must complete the full 3-week DLT window period to be considered evaluable for DLTs. Patients who discontinue from the study before the completion of the full 3-week (21 days) DLT window for reasons other than the occurrence of a DLT (e.g., withdrawal of consent, rapid tumor progression, death due to rapid tumor progression, AE that does not meet DLT criteria) will not be considered evaluable for DLTs and will be replaced.

Efficacy Population: The efficacy analysis for the Phase 1b (dose escalation) portion will be conducted on all DLT-evaluable patients, as defined in Section 6.2.2. The efficacy analysis for the Phase 2a (expansion phase) portion will be conducted on all patients who received at least one cycle of study treatment and have at least one evaluable post baseline tumor assessments.

